##### **6.2.1.4 Toxicity Management**

For the purpose of medical management, all adverse events and laboratory abnormalities that occur during the study must be evaluated by the investigator. The table of clinical toxicity grades from the NCI-CTCAE, Version 5.0 (available on CTEP home page: <http://ctep.info.nih.gov>) is to be used in the grading of adverse events and laboratory abnormalities that are reported as adverse events, each of which will be followed to satisfactory clinical resolution, except for CRS and NT which will be graded according to Lee et al (2019). AMG 340 has not been tested clinically in humans, so the adverse event profile in humans is not known.

Adverse events should be classified as pre-existing or as treatment-emergent adverse events:

- A treatment-emergent adverse event is defined as an adverse event not present prior to initiation of AMG 340 treatment, or an adverse event present prior to AMG 340 initiation that worsens in intensity and/or frequency after initiation of AMG 340 treatment.
- A pre-existing adverse event is an adverse event that does not meet these criteria. Subjects with pre-existing adverse events should be assessed for any underlying illness or other causes and treated as appropriate.

Subjects with treatment-emergent adverse events should also be assessed for intercurrent illness or other causes and treated as appropriate. If a treatment-emergent adverse event is unequivocally due to a subject's underlying malignancy or other extraneous cause, dosing with AMG 340 may be modified at the discretion of the Principal Investigator, following discussion with the Medical Monitors. If a treatment-emergent adverse event is not unequivocally due to the subject's underlying malignancy or other extraneous cause, regardless of whether there is a 'reasonable possibility' that the treatment-emergent adverse event is AMG 340-related, the dose of AMG 340 should be modified as follows:

- For subjects who have completed cycle 1 and have at least clinically or radiographically stable disease (SD, MR, PR or CR) but have experienced a reversible treatment-emergent adverse event, the dose of study drug can be delayed for up to 14 days after the scheduled dosing date. A subject for whom dosing is delayed > 14 days should be discontinued from the study.

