- During any cycle, if a subject develops an ANC < 500/ $\mu$ L, platelets < 10,000/ $\mu$ L, or a hemoglobin < 6.5 g/dL, blood samples must be collected every 3 days and study treatment withheld. Treatment may resume when ANC returns to  $\geq$  1,000/ $\mu$ L, platelet counts return to  $\geq$  50,000/ $\mu$ L or baseline platelet count levels (in subjects with baseline platelets < 50,000/ $\mu$ L), or hemoglobin returns to  $\geq$  8.0 g/dL.
- AMG 340 should be discontinued in any subject who experiences CRS, TLS, or a non-hematologic treatment-emergent adverse event that meets DLT equivalent criteria until resolution of the toxicity to  $\leq$  grade 1 or baseline; thereafter study drug may be resumed with one dose level reduction with Medical Monitor approval.

Up to 2 dose reductions are allowed to manage toxicity; thereafter toxicity will be deemed 'unacceptable' and the subject will be discontinued from therapy. Assessment schedules and cycles are fixed and should continue regardless of whether a dose is held.

While investigator discretion should be used for subject management with regards to toxicities, guidelines for management of CRS and NT are provided in [Table 6-6](#) and [Table 6-5](#).

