##### **6.2.1.4.1.1 Non-hematologic Dose-limiting Toxicity**

- Non-hematological adverse events grade  $\geq 3$  with the following exceptions:
  - Grade 3 or 4 isolated electrolyte abnormalities (ie, those occurring without clinical consequence) that resolve, with or without intervention, to grade  $\leq 1$  within 72 hours.
  - Grade 3 hyperglycemia responsive to optimal medical management within 72 hours.
  - Grade 3 nausea/vomiting/diarrhea responsive to optimal medical management within 72 hours.
  - Alopecia or vitiligo of any grade.
  - Grade 3 fatigue lasting  $< 10$  days.
  - Grade 3 fever (defined as a temperature  $\geq 40^{\circ}\text{C}$  with a duration of  $\leq 24$  hours occurring outside the context of CRS
  - Laboratory parameters of grade 3, not considered clinically relevant, and improved to grade (less than or equal to) 2 within 72 hours, will not be considered DLTs. Laboratory parameters with long half-lives, (ie, ALT, GGT, ALP, and lipase), will likewise not be considered DLTs if they are not considered clinically relevant, and improve to grade  $\leq 2$  within 7 days.
  - Adverse events that require a delay in initiation of the next scheduled cycle by  $> 14$  days.

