**Table 6-6. AMG 340 Dose Modification Guidelines for Adverse Events**

Grade	Description of Severity	Interruption/Delay	Specific Management	Re-start Guidance	Permanent Discontinuation
Infusion-related Reaction (continued)					
3	Prolonged (eg, not rapidly responsive to symptomatic medication and/or brief interruption of infusion); recurrence of symptoms following initial improvement; hospitalization indicated for clinical sequelae	Immediate interruption/delay until event has improved to grade $\leq 1$	Consider supportive therapy including steroids as clinically indicated.  Increase monitoring of vital signs as medically indicated until the subject is deemed medically stable.	
 
As for grade 2 infusion-related reaction, with the exception of mandatory dose modification: reduce to next lower dose
 
	If subject missed more than 2 consecutive doses of AMG 340
4	Life-threatening consequences; urgent intervention indicated	N/A	As for grade 3 infusion-related reaction	N/A	Immediately stop the infusion (if applicable) and permanently discontinue AMG 340 (monotherapy or in combination with pembrolizumab) therapy

Abbreviations and footnotes defined on last page of table.

Page 2 of 19

Table 6-6. AMG 340 Dose Modification Guidelines for Adverse Events

Grade	Description of Severity	Interruption/ Delay	Specific Management	Re-start guidance	Permanent Discontinuation
Neurologic Events					
≤ 2	For CRS-related neurological events, use ICANS grading and management system (Section 6.2.1.6.1.1)	Interrupt AMG 340 until the event improves to grade ≤ 1	Follow institutional guidelines for management	Resume AMG 340 no less than 72 hours after the initial observation of the grade 1 or 2 adverse event.	N/A
3			Administer corticosteroids per local practice	Resume AMG 340 no less than 7 days after the initial observation of the grade 3 adverse event. Reduce AMG 340 by 1 dose level.	
 
Initial grade 3 neurologic event does not improve to grade ≤ 1 within 7 days, OR
 
Grade 3 neurologic event reoccurs at the lower dose level within 7 days of re-initiation
 

4		--	--	--	Permanently discontinue AMG 340

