**Table 6-6. AMG 340 Dose Modification Guidelines for Adverse Events**

Grade	Interruption/ Delay	Specific Management	Re-start Guidance	Permanent Discontinuation
Gastrointestinal events related to AMG 340 (continued)				
≥ 3	Interruption/delay until event has improved to grade ≤ 1	Gastrointestinal (GI) toxicities should be managed according to the local standard of care and institutional guidelines	
 
Re-start possible if successfully managed and improvement to ≤ grade 1 in ≤ 14 days.
 
Delay of next infusion: 
 
≤ 7 days: Administer the delayed infusion (as long as the next scheduled infusion is > 6 days from delayed infusion) and follow the schedule of assessments for the cycle day on which the infusion was originally planned.
 
> 7 days: Skip the delayed infusion and resume schedule of assessments for the next scheduled infusion
 
 
 
Hospitalization: 48 hours
 
Dose modification: Resume at the same dose or reduce to next lower dose if clinically indicated
 
	If subject missed more than 2 consecutive doses of AMG 340 OR In case of reappearance of same event at grade 4 OR In case of repeat grade ≥ 3 event despite dose reduction

Page 12 of 19

Abbreviations and footnotes defined on last page of table.

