**Table 6-6. AMG 340 Dose Modification Guidelines for Adverse Events**

Grade	Interruption/Delay	Specific Management	Re-start Guidance	Permanent Discontinuation
Any other AMG 340-related events not meeting DLT criteria				
≥ 3	Interruption/delay required if deemed intolerable and/or clinically significant by the subject or investigator and not responding to appropriate medical management until event has improved to grade ≤ 1	N/A	
 
Re-start possible if successfully managed and improvement to ≤ grade 1 in ≤ 14 days.
 
Delay of next infusion: 
 
≤ 7 days: Administer the delayed infusion (as long as the next scheduled infusion is > 6 days from delayed infusion) and follow the schedule of assessments for the cycle day on which the infusion was originally planned.
 
> 7 days: Skip the delayed infusion and resume schedule of assessments for the next scheduled infusion
 
 
 
Hospitalization: 48 hours
 
Dose modification: Resume at the same dose or reduce to next lower dose if clinically indicated
 
	If subject missed more than 2 consecutive doses of AMG 340 OR In case of reappearance of same event at grade 4 OR In case of repeat grade ≥ 3 event despite dose reduction

Page 13 of 19

Abbreviations and footnotes defined on last page of table.

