**Table 6-6. AMG 340 Dose Modification Guidelines for Adverse Events**

Grade	Interruption/Delay	Specific Management	Re-start Guidance	Permanent Discontinuation
Any Non-AMG 340-related events				
4	Interruption/ delay required if deemed intolerable by the subject or investigator and not responding to appropriate medical management until event has improved to grade $\leq 1$	N/A	
 
Re-start possible if successfully managed and improvement to <math>\leq</math> grade 1 in <math>\leq 28</math> days.
 
Delay of next infusion: 
 
<math>\leq 7</math> days: Administer the delayed infusion (as long as the next scheduled infusion is <math>> 6</math> days from delayed infusion) and follow the schedule of assessments for the cycle day on which the infusion was originally planned.
 
<math>> 7</math> days: Skip the delayed infusion and resume schedule of assessments for the next scheduled infusion
 
 
 
Hospitalization: 48 hours
 
Dose modification: Resume at the same dose or reduce to next lower dose if clinically indicated
 
	If subject missed more than 2 consecutive doses of AMG 340 OR In case of reappearance of same event at grade 4

Page 14 of 19

Abbreviations and footnotes defined on last page of table.

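### After a DLT-equivalent gastrointestinal event, Section 6.2.1.4 ties restart to a dose reduction and Medical Monitor approval, while Table 6-6 allows the same dose and names no approval

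*Protocol*

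**What the plan says.** Section 6.2.1.4 (Toxicity Management) gives a list of dose actions, introduced by "the dose of AMG 340 should be modified as follows". The list applies to any treatment-emergent event not unequivocally due to the malignancy or another extraneous cause, whether or not a drug relationship is thought possible. One item covers CRS, TLS and non-hematologic events that meet DLT-equivalent criteria. Drug is stopped until the event is back to grade 1 or lower, or to baseline; "thereafter study drug may be resumed with one dose level reduction with Medical Monitor approval".

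Table 6-6 has its own row for gastrointestinal events related to AMG 340 of grade 3 or higher. Its restart column opens "Re-start possible if successfully managed and improvement to" grade 1 or lower within 14 days. It asks for 48 hours in hospital and then sets the dose: "Dose modification: Resume at the same dose or reduce to next lower dose if clinically indicated". The row does not mention the Medical Monitor.

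Section 6.2.1.4.1.1 treats non-hematologic events of grade 3 or higher as DLTs, with listed exceptions. The exception specific to nausea, vomiting and diarrhea is "Grade 3 nausea/vomiting/diarrhea responsive to optimal medical management within 72 hours".

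**The concern.** The two texts give different restart instructions for the same subject. Under Section 6.2.1.4 the subject comes back one dose level lower, with approval. Under the table row the investigator may restart at the same dose without asking. A site that looks up a gastrointestinal restart is likely to end at the table, because Section 6.2.2.1 refers readers there for restart guidance and does not mention Section 6.2.1.4.

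In a multicenter first-in-human study this could leave one subject re-exposed to the dose that caused a DLT-equivalent event and another, with the same event, reduced under sponsor oversight. Both sites could cite the protocol. Gastrointestinal toxicity is a listed potential safety concern in Table 2-2. Nausea (13 of 23 subjects), vomiting (12 of 23) and diarrhea (8 of 23) were among the most frequent events in Section 2.2.4.3.

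**Working it through.** The plan states no figure to reproduce. The check is mainly a comparison of texts.

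**1. Do the scopes overlap?** I read DLT-equivalent as meeting the criteria of Section 6.2.1.4.1.1. The exception quoted above removes only grade 3 nausea, vomiting or diarrhea that responds within 72 hours. Two AMG 340-related cases fall under both texts:

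| Event | Section 6.2.1.4 | Table 6-6, GI grade 3 or higher |
|---|---|---|
| Grade 3 diarrhea not controlled within 72 hours | One level down, with approval | Same dose allowed, no approval named |
| First grade 4 GI event | One level down, with approval | Same dose allowed, no approval named |

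**2. Is the GI row limited to non-DLT events?** Not in its wording. The next row is limited that way, by its heading "Any other AMG 340-related events not meeting DLT criteria"; the GI heading has no such limit. The GI row also calls for permanent discontinuation if the same event reappears at grade 4, so it contemplates restart after a severe first event.

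**3. Does the table state reductions and sponsor contact where it wants them?** Yes. The grade 3 infusion-reaction row follows the grade 2 row "with the exception of mandatory dose modification: reduce to next lower dose". The grade 3 neurologic row requires one level down. The grade 3 CRS row requires the medical monitor to be consulted before restart. The GI row does none of these.

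**4. Does any text rank the two?**

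- Section 6.2.1.4 refers to Table 6-6 only for CRS and neurotoxicity.
- Section 6.2.1.6.1.2 says continued-dosing decisions are driven by the DLT criteria and involve the Medical Monitor as appropriate. It sets no restart dose and does not mention the table.
- Section 6.2.2.1 requires medical supervision and dexamethasone at restart. The Medical Monitor agreement it mentions concerns the hospital stay.
- Table 6-6 footnote f requires written sponsor agreement for departures from the table's rules. Its marker is on the Monkeypox and COVID-19 column headings, and same-dose restart is the GI row's rule, not a departure from it.

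**5. A second place.** The grade 4 row "Any Non-AMG 340-related events" has the same dose wording. A grade 4 non-hematologic event judged unrelated, but not unequivocally extraneous, falls under both that row and Section 6.2.1.4.

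**6. How often might it arise?** Section 2.2.4.3 lists no GI event of grade 3 or higher among the 23 treated subjects at the 08 March 2022 cutoff, although the grade 3 list is introduced as a partial one. With no rate given, I assume a per-subject probability p of a DLT-equivalent GI event and use P(at least one) = 1 − (1 − p)^n:

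| Subjects counted | n | p = 1% | p = 2% | p = 5% |
|---|---|---|---|---|
| About 100 planned less 23 treated | 77 | 0.539 | 0.789 | 0.981 |
| Part B only (up to 40) | 40 | 0.331 | 0.554 | 0.871 |
| Part A only, if Part B does not open (60 − 23) | 37 | 0.311 | 0.526 | 0.850 |

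The expected number of subjects affected is n × p: 0.8, 1.5 and 3.9 for n = 77, and 0.4, 0.8 and 2.0 for n = 40.

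**The case against.** The best counter-argument is that the texts can be read together. Section 6.2.1.4 is the specific rule for DLT-equivalent events, and the GI row is the general one. Meeting DLT-equivalent criteria could itself count as the clinical indication for reducing. A site that reduces with approval complies with both, and silence in a table titled as guidelines does not waive an approval required elsewhere. The statement in Section 6.2.1.6.1.2 that dosing decisions follow the DLT criteria also points toward Section 6.2.1.4.

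All of that is fair, and it probably shows what was intended. It does not remove the permission to restart at the same dose. The GI row leaves the indication to judgment, and no sentence makes it yield.

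A second argument is that a silent same-dose restart is unlikely. Potential cycle 1 DLTs are discussed in Dose Level Review Team calls, the medical monitor is a required member of that team, and serious events reach the sponsor within 24 hours. The row itself stops treatment if the event reappears at grade 4 or if a grade 3 or higher event repeats despite reduction. These safeguards lower the risk, but none of them fixes the restart dose.

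A third argument concerns the probabilities. They give the chance that a relevant event occurs, not the chance that sites re-dose differently, which also needs recovery within 14 days and an investigator who chooses the same dose. That stands. The figures are upper limits on how often the conflict could matter, under assumed rates.

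**Conclusion.** The concern holds. For an AMG 340-related GI event meeting DLT-equivalent criteria, the protocol contains two stated rules that differ on restart dose and on approval, with no order of precedence. This is a conflict between rules, not a missing detail, and it should be corrected.

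The consequence is limited to subject safety and consistency of re-dosing. DLT classification, escalation decisions, MTD selection, sample size and power do not change. No conflict is claimed on the permitted number of reductions, on CRS, or on the row already limited to non-DLT events.

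The textual conclusion rests on reading DLT-equivalent as the Section 6.2.1.4.1.1 criteria; it does not depend on any event rate. The size does: at 1% to 5% per subject, the chance of at least one such event is 54% to 98% with 77 subjects remaining and 31% to 85% if only Part A continues. Subjects treated since the cutoff would lower the number remaining.

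**What to change.** In the Table 6-6 GI row for grade 3 or higher, restrict same-dose restart to events that do not meet DLT criteria. Add that after a DLT-equivalent GI event the subject restarts one dose level lower with Medical Monitor approval, citing Section 6.2.1.4.

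Alternatively, or in addition, put one precedence sentence in the table: for any non-hematologic event that meets DLT-equivalent criteria and is not unequivocally due to the malignancy or another extraneous cause, Section 6.2.1.4 sets the restart dose and approval unless the row is stricter. This version also covers the grade 4 row for unrelated events.

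The cost is one or two sentences in Table 6-6. Data collection, the DLT definition and the analyses stay as they are.

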#### **6.2.1.4.1 Dose Limiting Toxicity Definition for Dose Escalation**

The DLT observation period for dose escalation purposes is 21 days and covers the first complete treatment cycle of AMG 340 (1 dose of AMG 340; or up to 3 doses if priming has been implemented). Regular teleconferences will be conducted among the DLRT to examine/confirm potential DLTs, assess adverse events, and evaluate laboratory abnormalities. Events occurring outside the DLT window may be evaluated during these calls when making dose escalation decisions. A DLT is defined as a treatment emergent adverse event that is not unequivocally due to the subject's underlying malignancy or other extraneous cause and meets the criteria below.

The NCI-CTCAE version 5.0 will be used. DLT definitions are provided below.

